**Appendix 3: Cockcroft–Gault Calculation of Creatinine Clearance**

Subjects must have adequate renal function as evidenced by serum creatinine  $\leq 1.8$  mg/dL or calculated creatinine clearance  $\geq 50$  mL/min per the Cockcroft–Gault formula as defined below.

**Cockcroft–Gault Calculation for Creatinine Clearance**

Male	$\frac{(140 - \text{age}) \times \text{weight (kg)} \times 1.23}{\text{serum creatinine } (\mu\text{mol/L})} = \text{XX mL/min}$
Female	$\frac{(140 - \text{age}) \times \text{weight (kg)} \times 1.23 \times 0.85}{\text{serum creatinine } (\mu\text{mol/L})} = \text{XX mL/min}$

Source: Cockcroft DW, Gault MH. Prediction of creatinine clearance from serum creatinine. *Nephron*. 1976;16(1):31-41.

## Appendix 4: Common Terminology Criteria for Adverse Events (v4.03)

The National Cancer Institute's *Common Terminology Criteria for Adverse Events* (CTCAE v4.03 published 28 May 2009; v4.03: June 14, 2010) provides descriptive terminology to be used for AE reporting in clinical trials. A brief definition is provided to clarify the meaning of each AE term. To increase the accuracy of AE reporting, all AE terms in CTCAE version 4.03 have been correlated with single-concept, Medical Dictionary for Regulatory Activities (MedDRA®) terms.

CTCAE v4.03 grading refers to the severity of the AE. CTCAE Grades 1 through 5, with unique clinical descriptions of severity for each AE, are based on this general guideline:

### Common Terminology Criteria for Adverse Events v4.03 Grading

Grade	Status
1	Mild: asymptomatic or mild symptoms; clinical or diagnostic observations only; intervention not indicated.
2	Moderate: minimal, local, or noninvasive intervention indicated; limiting age-appropriate instrumental activities of daily living (ADL). a
3	Severe or medically significant but not immediately life-threatening: hospitalization or prolongation of hospitalization indicated; disabling, limiting self-care ADL. b
4	Life-threatening consequences: urgent intervention indicated.
5	Death related to adverse event.

a: Instrumental ADL refers to preparing meals, shopping for groceries or clothes, using the telephone, managing money, etc.

b: Self-care ADL refers to bathing, dressing and undressing, feeding self, using the toilet, taking medications, and not bedridden.

Source: Cancer Therapy Evaluation Program, NCI. CTCAE v4.03. Available from: [http://ctep.cancer.gov/protocolDevelopment/electronic\\_applications/docs/ctcaev4.pdf](http://ctep.cancer.gov/protocolDevelopment/electronic_applications/docs/ctcaev4.pdf).

For further details regarding MedDRA, refer to the MedDRA website:  
<http://www.meddramsso.com>.

CTCAE v4.03 is available online:  
[http://ctep.cancer.gov/protocolDevelopment/electronic\\_applications/docs/ctcaev4.pdf](http://ctep.cancer.gov/protocolDevelopment/electronic_applications/docs/ctcaev4.pdf).

2 LIST OF ABBREVIATIONS AND DEFINITIONS OF TERMS (TO BE ADDED)

| Abbreviation | Term |
|-----------------------|---|
| AE | adverse event |
| ATC | anatomical therapeutic class |
| AUC | area under the concentration-time curve |
| BLQ | below limit of quantification |
| BMI | body mass index |
| BOR | best overall response |
| BSA | body surface area |
| CxDy | Cycle x Day y |
| CBR | clinical benefit rate |
| CI | confidence interval |
| CL | total body clearance |
| CL _r | renal clearance |
| Cmax | maximum observed plasma concentration |
| CR | complete response |
| CRF | case report form |
| CSR | clinical study report |
| CTCAE | Common Terminology Criteria for Adverse Events |
| CV | coefficient of variation |
| DCR | disease control rate |
| DLT | dose-limiting toxicity |
| DOR | duration of response |
| ECG | electrocardiogram |
| ECOG | Eastern Cooperative Oncology Group |
| EOT | end of treatment |
| FAS | full analysis set |
| fe | fraction excreted |
| ¹⁸ FDG-PET | ¹⁸ fluorodeoxyglucose positron emission tomography |
| irCR | immune-related complete response |
| irNE | (immune-related) not evaluable |
| irPD | immune-related progressive disease |
| irPR | immune-related partial response |
| irSD | immune-related stable disease |
| irRECIST | immune-related RECIST |
| MedDRA | Medical Dictionary for Regulatory Activities |
| MTD | maximum tolerated dose |
| ORR | overall response rate |
| OS | overall survival |
| PD | pharmacodynamic |
| PFS | progression-free survival |

| | |
|------------------|--|
| PK | pharmacokinetic |
| PR | partially response |
| PT | preferred term |
| Q1 | first quartile (25 percentile) |
| Q3 | third quartile (75 percentile) |
| R2PD | recommended phase 2 dose |
| Rac | accumulation ratio |
| RECIST | Response Evaluation Criteria In Solid Tumors |
| SAE | serious adverse event |
| SAP | statistical analysis plan |
| SD | stable disease or standard deviation |
| SE | standard error |
| SI | Système International |
| SOC | system organ class |
| t _{1/2} | terminal elimination half-life |
| TEAE | treatment-emergent adverse event |
| TLG | tables, listings, and graphs |
| t _{max} | time to maximum concentration |
| TTR | time to response |
| V _d | volume of distribution |
| WHO | World Health Organization |

3 INTRODUCTION

The purpose of this statistical analysis plan (SAP) is to describe the procedures and the statistical methods that will be used to analyze and report results for Eisai Protocol E7046-G000-101 Amendment 01 dated 30 December 2015.

3.1 STUDY OBJECTIVES

3.1.1 Primary Objective(s)

The primary objectives of the study are to:

- Assess the safety/tolerability profile of E7046 as a single agent administered orally once daily, continuously in 21-day cycles, in subjects with selected advanced and/or recurrent malignancies.
- Determine the maximum tolerated dose (MTD) and/or the recommended Phase 2 dose (RP2D) of E7046.

3.1.2 Secondary Objective(s)

The secondary objectives of the study are to:

- Evaluate the pharmacokinetic (PK) profile of E7046.
- Evaluate the objective response rate (ORR) according to the immune-related RECIST (irRECIST) in subjects treated with E7046 with selected tumor types with high level of myeloid infiltrate.
- Evaluate the following additional efficacy endpoints according to the irRECIST: time to response (TTR), duration of response (DOR), progression-free survival (PFS), disease control rate (DCR), and clinical benefit rate (CBR).

3.1.3 Exploratory Objective(s)

The exploratory objectives of the study are to:

- Explore efficacy according to Response Evaluation Criteria In Solid Tumors (RECIST) 1.1, using the following endpoints: ORR, TTR, DOR, PFS, DCR, and CBR.
- Assess overall survival (OS).
- Explore the pharmacodynamic effect of E7046 on selected immune cell populations and selected biomarkers in tumor infiltrate and in peripheral blood.
- Explore ¹⁸FDG-PET as a biomarker of response.
- Explore the pharmacokinetic/pharmacodynamic (PK/PD) relationship.

3.2 OVERALL STUDY DESIGN AND PLAN

This is an open label, multicenter, Phase 1 study that will be conducted in 2 parts: a dose escalation part and a cohort expansion part. The objective of the dose escalation part is to assess the safety and tolerability and determine the MTD and/or RP2D of E7046. In the cohort

expansion part an additional 6 to 16 subjects will be treated at the RP2D to further characterize safety, efficacy, PK, and PD. E7046 is a novel cancer immune therapy and as this is the first study in humans therefore a cautious approach in the first cohort of patients is prudent. Staggered start of dosing in the first cohort will thus be implemented to ensure exposure of a limited number of subjects in the initial dosing cohort.

A major consideration was that the toxicities of E7046 are likely to be moderate in the dose range planned and an MTD may not be reached (according to preclinical results). It is anticipated that the RP2D will be selected based on integrated evaluation of safety, tolerability, clinical benefit, PK, and PD data, collected from all dose levels tested. Accordingly, a modification of the standard 3+3 design was selected, where dose cohorts of 6 subjects will be enrolled at each of the 4 dose levels to be tested so as to provide sufficient data for selecting RP2D in the absence of an MTD.

The study will consist of three phases for each subject: Pretreatment Phase, Treatment Phase, and Extension Phase.

A schematic of the 3 Phases is shown in Figure 1.

Figure 1 Study Design

| PHASE | Pretreatment | | Treatment | | | Extension | | |
|--------|------------------------|----------|-------------------|----|---|-----------|-------------------|------------|
| PERIOD | Screening | Baseline | Treatment Cycle 1 | | Treatment Continuation (Cycle 2 and beyond) | | EOT | Follow -Up |
| Day | -28 to -1 | -3 to -1 | D1 | D8 | D15 | D1 | D8 (C2-6 only) | |
| VISIT | 1 | 2 | 3 | 4 | 5 | 6, 8 etc | 7, 9 etc | 98 |
| | EOT = End of Treatment | | | | | | | |

The schedule of procedures/assessments for the study is presented in Section 13.1.

The study may be cut off for the data analysis and report when the study achieves its primary objective, i.e., the last subject completes his/her first cycle of study drug/treatment phase, or the sponsor and primary investigator of the study may determine the cutoff date for the analysis based on the enrollment and overall progress of the study.

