### 9.1.3.3 Extension Phase

The Extension Phase consists of 2 periods:

- **Treatment Continuation Period**, during which subjects will continue in Cycle 2 and beyond to receive the same treatment they received during the Treatment Phase.  
The **Treatment Continuation** period will start at the end of the Treatment Phase and will end with the completion of the Off-Treatment Visit (which will occur within 30 days after the last administration of the study drug). It consists of study drug treatment on a 21-day cycle, regardless of dose interruptions. Subjects will undergo safety and efficacy assessments as defined in Schedule of Procedures ([Section 9.5.6.1](#)) . Subjects will discontinue the study drug and become Off-Treatment at the time of disease progression, development of unacceptable toxicity, withdrawal of consent or termination of the study program.
- A **Follow-Up Period**, for study assessments after discontinuation from study treatment.  
The **Follow-up Period** will begin the day after the Off-Treatment Visit and will continue as long as the study subject is alive until the completion of the primary analysis, unless the subject withdraws consent or until the sponsor terminates the study. Subjects, who discontinue study treatment without disease progression will continue to be followed and undergo tumor assessments every 6 weeks until disease progression or until the start of another anticancer treatment. In the follow-up period, subjects will be treated by the investigator according to the prevailing local standard of care. Subjects will be followed every 12 weeks ( $\pm 1$  week) for survival, performance status and subsequent anticancer treatments. The sponsor may decide to terminate survival follow-up anytime during the Extension Phase or when all subjects have discontinued study treatment.

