## 9.7 Statistical Methods

All statistical analyses will be performed by the sponsor or designee after the study is completed and the database is locked and released. Statistical analyses will be performed using WinNonlin and SAS software or other validated statistical software as required. Details of the statistical analyses will be included in a separate statistical analysis plan (SAP).

Descriptive statistics will be used for continuous variables using n, mean, standard deviation (SD), median, Q1 (25th percentile), Q3 (75th percentile), minimum, and maximum, unless otherwise specified. Categorical variables will be summarized as number (percent) of subjects.

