### 9.7.1 Statistical and Analytical Plans

For purposes of the final analysis, data cutoff will occur when the last enrolled subject completes 6 cycles of treatment (ie all subjects have been followed by a minimum of 6 cycles) or subjects discontinue early, whichever occurs first. The statistical analyses of study data are described in this section. Further details of the analytical plan will be provided in the SAP, which will be finalized before database lock.

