### 9.7.3 Interim Analysis

No interim analyses are planned.

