7 CHANGES IN THE PLANNED ANALYSES

This SAP is in accordance with Clinical Study Protocol v1.0, dated 07 May 2015. No changes to the planned analysis will be applied in this SAP.

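### SAP 3.2 permits a data cutoff after the last subject's Cycle 1 or at discretion, against six cycles in Protocol 9.7.1, and neither cutoff guarantees the 24 weeks that stable disease needs to count in CBR

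*SAP*

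**What the plan says.** **Cutoff in the protocol.** Section 9.7.1 says that for the final analysis "data cutoff will occur when the last enrolled subject completes 6 cycles of treatment", "or subjects discontinue early, whichever occurs first". Section 9.7 places all statistical analyses "after the study is completed and the database is locked and released". Section 9.7.3 states: "No interim analyses are planned".

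**Cutoff in the SAP.** Section 3.2 allows the cutoff for analysis and reporting once the study achieves its primary objective, which it explains as the point when "the last subject completes his/her first cycle of study drug/treatment phase". It also gives a discretionary alternative: "sponsor and primary investigator of the study may determine the cutoff date for the analysis based on the enrollment and overall progress". That alternative carries no minimum follow-up. SAP Section 6 lists interim analyses as not applicable.

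**CBR.** Protocol 9.7.1.1 and SAP 5.4.1 count irSD toward CBR only if it lasts at least 24 weeks. SAP 5.4.1 measures irSD from first dose to the earliest of irPD, death and the last evaluable tumor assessment. CBR is a simple proportion, summarized by dose group.

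**Analysis set.** SAP 5.4 runs all efficacy analyses on the Response Evaluable Set, which requires at least one post-baseline evaluation (SAP 5.2.1). Protocol 9.7.1.2 names the Full Analysis Set as primary for efficacy.

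**Scans.** Protocol 9.5.2 schedules tumor assessments every 6 weeks, during the sixth week counted from C1D1. Under Protocol 9.1.3.3, subjects who stop treatment without progression "will continue to be followed and undergo tumor assessments every 6 weeks until disease progression" or another anticancer treatment starts.

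**The concern.** The two documents give different cutoffs for what appears to be the same analysis, and one SAP option has no fixed rule at all. In an open-label study, a cutoff date chosen while results are visible invites a question that a fixed rule avoids.

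The cutoff matters most for CBR. PFS is handled by Kaplan-Meier with censoring, so short follow-up does not turn a stable subject into a failure. CBR has no such provision. Because irSD duration ends at the last evaluable scan, a subject who is stable and simply has not been followed for 24 weeks is classified in the same way as one whose disease control ended early. The resulting error is always downward. At the protocol cutoff it falls on the subjects enrolled last, who belong to the expansion cohort that Protocol 9.1.2 sets up partly to evaluate efficacy at the RP2D.

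**Working it through.** **Inputs**
- Cycle length: 21 days, regardless of dose interruptions (Protocol 9.1.3.3).
- Protocol cutoff: 6 cycles. SAP Cycle 1 option: 1 cycle.
- CBR requirement: 24 weeks. Minimum irSD for best overall response: 5 weeks (SAP 5.4.1).
- Scan in week w: Days 7(w-1)+1 to 7w.
- Confirmation of response: at least 4 weeks later.
- Group sizes: 6 per escalation cohort, 6 to 16 in expansion.

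The plan does not convert its cutoffs to days, so there is no stated follow-up figure to reproduce. The stated maximum sample size does reproduce: 4 × 6 + 16 = 40.

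**Step 1: follow-up of the last subject**
- Requirement: 24 × 7 = 168 days.
- Protocol: 6 × 21 = 126 days; shortfall 168 - 126 = 42 days.
- SAP Cycle 1 option: 1 × 21 = 21 days; shortfall 168 - 21 = 147 days.
- SAP discretionary option: no minimum.

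**Step 2: scan windows**
- Week 6: Days 36-42. Week 12: Days 78-84. Week 18: Days 120-126. Week 24: Days 162-168.
- Day 126 reaches the Week 18 scan but not Week 24. Day 21 precedes every scheduled scan.

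**Step 3: who is affected**

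Let k be the number of days by which a subject was first dosed before the last subject. At cutoff that subject is on Day 126 + k (protocol) or Day 21 + k (Cycle 1 option). The ranges run from the first to the last day of each scan window, and an in-window Week 24 scan is taken to qualify.
- Protocol: the Week 24 scan is reached when k is at least 162 - 126 = 36 to 168 - 126 = 42. A stable subject with smaller k is scored as not meeting CBR.
- Cycle 1 option, Week 24: k must be at least 162 - 21 = 141 to 168 - 21 = 147.
- Cycle 1 option, any scheduled scan: k must be at least 36 - 21 = 15 to 42 - 21 = 21. Below that, the subject leaves the Response Evaluable Set, or counts as a failure if the Full Analysis Set is used or, for ORR, if the nonresponder sentence in SAP 5.4.1 is applied.
- Scanned, still-stable subjects are therefore misclassified under the Cycle 1 option for k from about 15-21 up to about 141-147.
- Confirmed response under the Cycle 1 option: the earliest confirmation is Day 36 + 28 = 64 to Day 42 + 28 = 70, so k must be at least 64 - 21 = 43 to 70 - 21 = 49. If confirmation waits for Week 12, k must be at least 78 - 21 = 57 to 84 - 21 = 63.

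**Step 4: effect of one misclassified subject**

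CBR is reported by dose group, so the RP2D group holds 6 + 6 = 12 to 6 + 16 = 22 subjects.
- 1/12 = 8.3 percentage points; 1/22 = 4.5 percentage points.

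**The case against.** **SAP 3.2 may describe an escalation-only review.** It ties the cutoff to the primary objective, the primary endpoints are labelled for the Dose Escalation part (Protocol 9.7.1.1, SAP 5.1.1), and Protocol 9.1.1.4 selects the RP2D after the last escalation subject completes the Treatment Phase. This stands as a possible reading, because the SAP does not define which last subject it means. On that reading the Cycle 1 option does not touch the expansion cohort. But SAP 3.2 does not limit itself to escalation or to safety data, neither document plans an interim analysis, and the discretionary option remains. The wording is permissive, and the point is only that it permits the early cutoff.

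**Eighteen weeks of follow-up with a 24-week endpoint is a limitation, not an error.** This also stands. Nothing requires every subject to have 24 weeks, so a reader who infers that the protocol cutoff must move later goes beyond the documents. What remains is that the CBR rule counts short follow-up as failure.

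**Stronger readings that the documents do not support**
- *DCR is understated under the Cycle 1 option.* Not on the Response Evaluable Set: unscanned subjects leave the denominator, and a stable Week 6 scan falls 35 to 41 days after first dose, which meets the 5-week (35-day) minimum.
- *SAP Section 7 contradicts SAP 3.2.* It says "No changes to the planned analysis will be applied in this SAP", but with reference to Protocol v1.0, which is not available here; SAP Section 3 cites Amendment 01. The statement proves nothing about the cutoff.
- *A Week 24 scan can never satisfy 24 weeks.* Counting elapsed days (day minus 1), the window gives 161-167 days and falls short. Counting inclusively, a Day 168 scan qualifies. The SAP shows no convention and leaves derivation rules to separate documents (Section 9), so only the ambiguity can be claimed.

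**Conclusion.** The cutoff conflict is real and should be fixed, and the CBR shortfall exists under both documents. For the last subject it is 42 days at the protocol cutoff and 147 days under the Cycle 1 option. The early-discontinuation clause can shorten the protocol follow-up further, even though subjects who stop without progression stay on 6-weekly scans.

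Only subjects who have a post-baseline scan, no confirmed response and no progression at cutoff are misclassified. Subjects already confirmed as responders or progressed are unaffected, and subjects enrolled early enough have their 24 weeks.

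The day ranges assume scans on schedule, a cutoff on the day the cycle ends, and acceptance of an in-window Week 24 scan. The Cycle 1 ranges also assume that the last enrolled subject is meant. The 4.5 to 8.3 points assume that escalation and expansion subjects at the RP2D are reported as one dose group and are all evaluable. The number of subjects affected cannot be given, because no accrual rate is stated. These endpoints are secondary and descriptive, with no hypothesis test, so the consequence is a CBR that is too low and hard to interpret, not a false inference.

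**What to change.** 1. In SAP 3.2, remove the Cycle 1 and discretionary options as the final-analysis cutoff and use the Protocol 9.7.1 cutoff. If an escalation-only review was meant, label it as such, define the last subject as the last escalation subject, and limit it to DLT and RP2D data.
2. In SAP 5.4.1, report CBR among subjects first dosed at least 168 days before cutoff, whether or not they discontinued early, alongside the figure for the full analysis set. Such a subject is on Day 169 or later at cutoff, after the Week 24 window closes on Day 168. Selection depends only on the first-dose date, not on outcome.
3. State in SAP 5.4.1 that a Week 24 scan within its protocol window (Days 162-168) showing no irPD satisfies the 24-week requirement.

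The cost is wording in SAP 3.2 and 5.4.1, with no extra visits or scans. The downside of item 2 is a smaller denominator for that CBR figure.

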4 DETERMINATION OF SAMPLE SIZE

The sample size of approximately 40 subjects is considered adequate for the purposes of selecting a dose.

The expected sample size for the dose escalation part of this trial will be up to 24 patients. Per the dose escalation design adopted and modified from the traditional 3+3 design, there will be a

maximum of 4 planned cohorts and there will be 6 subjects each cohort to allow for adequate assessment in tolerability, clinical benefit, PK, PD data and integrated evaluation of safety so as to select RP2D. Additional 6-16 subjects will be enrolled in the expansion cohort to confirm RP2D.

The dose escalation part and the extension part yield a total maximum sample size of 40 subjects.

5 STATISTICAL METHODS

All descriptive statistics for continuous variables will be reported using mean, standard deviation (SD), median, Q1, Q3, minimum and maximum; otherwise will be specified. Categorical variables will be summarized as number (percentage) of subjects.

5.1 STUDY ENDPOINTS

5.1.1 Primary Endpoint(s)

Primary Endpoints (Dose Escalation Part):

- Safety/tolerability profile of E7046.
- MTD and/or the RP2D.

5.1.2 Secondary Endpoint(s)

Secondary Efficacy Endpoints:

- Objective response rate (ORR)

The ORR is the proportion of patients achieving a best overall response (BOR) of confirmed partial or complete response (irPR + irCR), according to the irRECIST (Section 13.2) from first dose date until disease progression/recurrence. Subjects who do not have a tumor response assessment for any reason will be considered nonresponders and will be included in the denominator when calculating the response rate.

- Duration of response (DOR)

The DOR is defined as the time from the date of first documented confirmed irCR/irPR until the first documentation of confirmed disease progression or death, whichever comes first.

- Progression-free survival (PFS)

The PFS is defined as the time from first dose date to the date of the first documentation of confirmed disease progression or death (whichever occurs first) using irRECIST. The PFS is also defined as the event that a subject is alive without confirmed disease progression at a specific evaluation time point. The censoring rule for events will be defined in the SAP.

- Disease control rate (DCR)

The DCR is the proportion of patients achieving irPR + irCR + irSD from first dose date until disease progression/recurrence.

- Clinical benefit rate (CBR)

The CBR is the proportion of patients achieving irPR + irCR + durable irSD [lasting at least 24 weeks] from first dose date until disease progression/recurrence.

